6.3. Method of Assigning Subjects to Treatment Groups

Subjects who are candidates for screening into the study will be evaluated for eligibility by the Investigator to ensure that the inclusion and exclusion criteria initially have been satisfied. The Unblinded Pharmacist will register the subject in the IVRS system, and the IVRS system will assign a sequential and unique subject number. Once a subject number has been assigned, it cannot be reused.

Prior to randomization, the Investigator will ensure that the subject continues to meet the inclusion and exclusion criteria and is eligible for study participation.

Once a subject is deemed by the Investigator to be eligible, the unblinded pharmacist will access the IVRS system for randomization and study drug assignment.

6.4. Blinding

All study personnel, with the exception of the unblinded site pharmacist, will be blinded to the treatment allocation a subject is randomized to. It is imperative that this blinding be maintained during the dispensing of investigational product.

6.4.1. Procedures for Breaking the Blind

The treatment assignment must not be broken during the study except in emergency situations where the identification of study drug is required for further treatment of the subject. Unblinding of the individual subject's treatment by the investigator will be limited to medical emergencies or urgent clinical situations in which knowledge of the subject's study treatment is necessary for clinical management. In such cases, the Investigator should use his/her best judgment as to whether to unblind without first attempting to contact the Medical Monitor to discuss and agree to the need for unblinding. If the Investigator determines that it is not necessary to unblind immediately, he/she will first attempt to contact the Medical Monitor to discuss and agree to the need for unblinding. If the Investigator has tried but is unable to reach the Medical Monitor, he/she should use his/her best judgment, based on the nature and urgency of the clinical situation, and may proceed with unblinding without having successfully reached and discussed the situation with the Medical Monitor.

6.5. Study Drug Supply

PRM-151 Solution for Injection is a 20 mg/mL solution of PRM-151 in 10 mM sodium phosphate, 5% (w/v) sorbitol, and 0.01% (w/v) polysorbate 20 with a pH of 7.5. Each vial of PRM-151 Solution for Injection contains 160 mg of PRM-151 in 8.0 mL of solution.

Placebo consists of an infusion of sterile physiologic saline, matched to PRM-151 in total volume.

6.6. Packaging and Labeling

PRM-151 is supplied in 10 ml single use vials as a clear to opalescent, sterile 20.0 mg/mL solution 10 mM sodium phosphate, 5% (w/v) sorbitol, and 0.01% (w/v) polysorbate 20 with a pH of 7.5. Each vial contains 8 ml PRM-151 (160 mg of PRM-151).

Study drug will be labeled investigational. Study drug labels will not bear any statement that is false or misleading in any manner or represents that the study drug is safe or effective for the purposes for which it is being investigated.

6.7. Storage and Accountability

PRM-151 will be provided to the clinical site in a temperature controlled, monitored container. Investigational product should be stored under refrigerated conditions (2°C-8°C [35.6°F-46.4°F]) and protected from light. Vigorous mixing or vortexing should be avoided.

Investigational product will be dispensed at the study site and stored in a locked storage area. The disposition of all investigational product delivered to a Principal Investigator must be recorded on a subject-by-subject basis by completing the Clinical Trial Material Accountability Log. The date and time of administration of the investigational product must be documented on the appropriate eCRF.

The unblinded pharmacist must ensure that all documentation regarding investigational product receipt, storage, dispensing, loss/damaged and return of used/unused product is complete, accurate, and ready for review at each monitoring visit and/or audit. The sites must ensure that the investigational product is available for the monitor to inventory and prepare for return shipment to the Sponsor or designee, if required.

All packing slips and other shipment documentation must be retained as well as any investigational product return forms. See the Pharmacy Manual for additional details.

6.8. Rationale for the Dose(s) Selected

In a multiple ascending dose study (PRM151F-12GL), PRM-151 administered IV on Days 1, 3, 5, 8, and 15 to subjects with IPF was well tolerated at doses up to 10 mg/kg. Plasma levels of PRM-151 (C_{max} and AUC) were dose proportional across the range of doses from 1 to 10 mg/kg. PRM-151 had a half-life of 21 to 44 hours. The study did not demonstrate a dose response, but was not intended to do so. Based on these findings, a PRM-151 dose of 10 mg/kg was selected for investigation in the current study.

Preclinical dose ranging studies and in vitro potency assays indicate that the effective dose range in humans may be .2-10 mg/kg. Ten mg/kg was selected for this study because it was safe and resulted in a reduction in bone marrow fibrosis in 11 out of 24 subjects with myelofibrosis treated with PRM-151 10 mg/kg either weekly or every 4 weeks.

7. STUDY PROCEDURES

Detailed descriptions of subject evaluations required for this protocol are described in this section. These evaluations will be performed during the indicated days and weeks of the study as described in Section 7 and in the Schedule of Events (Appendix A).

All data collected are to be recorded on source documents and entered into the appropriate eCRF page.

The Investigator at the clinical trial site is responsible for maintaining a record of all subjects pre-screened, screened, and enrolled into the study.

All subjects must provide written informed consent before the performance of any study procedures.

7.1. Informed Consent

Prior to conducting any study-related procedures, written informed consent must be obtained from the subject or the subject's legally authorized representative.

The nature, scope, and possible consequences, including risks and benefits, of the study will be explained to the subject by the Investigator or designee in accordance with the guidelines described in Section 9.1. Documentation and filing of informed consent documents should be completed according to Section 10.5.

7.2. Study Entrance Criteria

At Screening, each subject assessed for eligibility against the study entrance criteria. Subjects who do not meet the study entrance criteria will not be allowed to participate in the study. The reason(s) for the subject's ineligibility for the study will be documented.

7.3. Demographics

Subject demographic information including gender, age, date of birth, race, ethnicity and number of years since diagnosis of IPF will be collected prior to the subject receiving the first dose of PRM-151.

7.4. Past Medical History

Medical history will be recorded in the eCRF. Any relevant and/or significant previous or existing medical condition(s) that occurred within 5 years prior to time of informed consent) should be reported as medical history. Prior and current therapies for IPF will be recorded in the eCRF.

7.5. Height and Weight

Height will be recorded at Screening for all subjects. Weight will be recorded at all dosing visits for all subjects.

7.6. Laboratory Variables

Clinical laboratory tests will be performed by the local clinical laboratory facility.

7.6.1. Hematology and Clinical Chemistries

Blood samples for hematology, clinical chemistries and coagulation are to be collected as per the schedule of events (Appendix A).

The following laboratory variables are to be measured:

Hematology; Hematocrit, Platelet count, White blood cell (WBC) count, Red blood cell (RBC) count, Hemoglobin, Lymphocytes, Eosinophils, Neutrophils, Monocytes, Basophils.

Serum Chemistries and Liver Function Tests; Chloride, Potassium, Blood urea nitrogen (BUN), Creatinine, Albumin, Aspartate aminotransferase (AST), Total bilirubin, Sodium, Bicarbonate (CO₂), Calcium, Glucose, Alkaline phosphatase (ALK), Alanine aminotransferase (ALT), Total protein.

Coagulation Tests: Prothrombin time (PT), Partial Thromboplastin time (PTT), International Normalized Ratio (INR)

7.6.2. ECG and Cytokines

ECG and cytokines will be collected at baseline prior to PRM-151 dosing. Following the baseline assessment, ECG and cytokines will only be collected in the event of an infusion related reaction (IRR) as soon as possible after stabilization of the subject.

7.6.3. Pregnancy Testing

Serum pregnancy testing is required for female subjects of child-bearing potential. A female of childbearing potential is a sexually mature woman who has not undergone a hysterectomy, bilateral oophorectomy, or tubal ligation or is not naturally postmenopausal (i.e., has had menses at any time within the previous 24 months).

Pregnancy testing is to be performed during Screening. Pregnancy testing should be repeated during treatment any time pregnancy is suspected.

During Screening, results must be reviewed and confirmed to be negative for the subject to be eligible for enrollment in the study. If positive pregnancy test results are obtained after the start of study drug treatment, study drug is to be unblinded and discontinued. Pregnancies are to be reported and followed as described above.

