9. Women of child bearing potential (WCBP), defined as a sexually mature woman not surgically sterilized or not post-menopausal for at least 24 consecutive months if ≤ 55 years or 12 months if > 55 years, must have a negative serum pregnancy test within four weeks prior to the first dose of study drug and must agree to use highly effective methods of birth control throughout the study and up to 30 days after the study for WOCBP and up to 90 days for partners of child bearing potential of male participants. Highly effective methods of contraception include combined (estrogen and progestogen containing) hormonal contraception associated with inhibition of ovulation by oral, intravaginal, or transdermal administration; progestogen-only hormonal contraception associated with inhibition of ovulation by oral, injectable, or implantable administration; intrauterine device (IUD); intrauterine hormone-releasing system (IUS); bilateral tubal occlusion; partner vasectomy, and total abstinence (only if total abstinence is the preferred method and usual lifestyle of the subject). Adequate contraceptive use should be continued until 28 days after the final dose of the study drug.

-
10. Subject has a life expectancy of at least 9 months
 11. Subject, according to the investigator's best judgment, can comply with the requirements of the protocol.
 12. Subject and the treating physician considered all medicinal treatment options and / or possibly a lung transplantation prior to considering participation in the study
 13. If the subject is on a lung transplant list, the Investigator anticipates the subject will complete the study prior to transplant.
 14. Subject has provided written informed consent to participate in the study.

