5.2. Withdrawal and Replacement of Subjects

The Investigator may withdraw a subject from the study for any of the following reasons:

- Subject, Investigator, or Sponsor request.
- Protocol violation.
- AE.
- Pregnancy (mandatory).
- Progression of disease that, in the opinion of the Investigator, precludes further study drug treatment.
- Subject decision. A subject may withdraw consent to participate in the study at any time.

The reason for study withdrawal is to be documented in the subject's source documents and electronic case report form (eCRF).

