7.10. Efficacy Measurements

On all dosing days, dosing will occur after all safety and efficacy assessments scheduled for that visit are complete.

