12. APPENDIX A SCHEDULE OF EVENTS

		Week 0 (+/-1day)		W4, W8, W12, W16, W20,W24 (+/- 3d)	W28/ EOS (+/- 3d)	W28 (+/- 3d)		W32 (+/- 3d)	W36 (+/- 3d)	W40 (+/- 3d)	W44 (+/- 3d)	W48 (+/- 3d)	W52 (+/- 3d)	Week 56 (+/-3days)	
		Baseline Dosing Day 1	Dosing Days 3, 5	Dosing Day 1	Dosing Day 1	Dosing Day 1	Dosing Days 3, 5	Dosing Day 1	Baseline Dosing Day 1						
Informed Consent	x														
Demographics	x														
Past Medical History	x														
Inclusion/Exclusion	x	x													
Vital Signs (pre and post dose and every 15 minutes for the duration of the infusion)	x	x	x	x	x	x	x	x	x	x	x	x	x	x	x
Physical Exam[1]	x	x		x	x	x	x	x	x	x	x	x	x	x	x
Height (cm)	x														
Weight (kg)	x	x		x		x	x	x	x	x	x	x	x	x	x
Prior/Concomitant Medications	x	x	x	x	x	x	x	x	x	x	x	x	x	x	x
Special list of excluded medications	x	x	x	x	x	x	x	x	x	x	x	x	x	x	x
AE/SAE Assessment		x	x	x	x	x	x	x	x	x	x	x	x	x	x
ECG & Cytokines (ONLY in the event of an IRR after Baseline)		x	x	x			x	x	x	x	x	x	x	x	x
Efficacy Assessment[2]															
Patient Reported Outcomes; K-BILD & LCQ	x	x		x	x	x		x	x	x	x	x	x		

Pulmonary Function Tests (PFTs)	x	x		x	x	x		x	x	x	x	x	x		
DLCO[3]	x	x			x	x									
FRC & TLC by nitrogen washout method[4]	x	x			x	x									
HRCT (with spirometry at select sites)[5]		x			x	x									
6-minute walk test	x	x		x	x	x		x	x	x	x	x	x		
Pregnancy test Each visit after V4 for all WOCBP	x														
Complete Blood Count	x	x		x	x	x				x			x		
Chemistry, BUN/creatinine	x	x		x	x	x				x			x		
Coagulation	x	x		x	x	x				x			x		
Status of baseline genetic characteristics[6]		x													
Anti-pentraxin 2 antibodies (ADA), Pre-dose		x		x	x	x				x			x		
Pentraxin-2 levels, Pre-dose		x		x	x	x				x			x		
Exploratory laboratory assessments (optional)[7]		x			x	x									
PRM-151 dosing[8]		x	x	x		x	x	x	x	x	x	x	x	x	x

		W60	W64	W68	W72	W76	W80	Week 84		W88	W92	W96	W100	W104	W108	
		(+/- 3d)	(+/-3days)	(+/- 3d)												
		Dosing Day 1	Baseline Dosing Day 1	Dosing Days 3, 5	Dosing Day 1											
Informed Consent	x															
Demographics	x															
Past Medical History	x															
Inclusion/Exclusion	x															
Vital Signs (pre and post dose and every 15 minutes for the duration of the infusion)	x	x	x	x	x	x	x	x	x	x	x	x	x	x	x	x
Physical Exam[1]	x	x	x	x	x	x	x	x	x	x	x	x	x	x	x	x
Height (cm)	x															
Weight (kg)	x	x	x	x	x	x	x	x		x	x	x	x	x	x	x
Prior/Concomitant Medications	x	x	x	x	x	x	x	x	x	x	x	x	x	x	x	x

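### Section 7.6.3 schedules no pregnancy test after Screening, while the Appendix A row label calls for repeats from an undefined V4; criterion 9 also gives two female contraception end points

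*Protocol*

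**What the plan says.** Section 7 opens by saying that evaluations are carried out "as described in Section 7 and in the Schedule of Events (Appendix A"), and gives neither source precedence.

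- **Section 7.6.3:** a serum test at Screening for women of child-bearing potential, then "Pregnancy testing should be repeated during treatment any time pregnancy is suspected". No scheduled repeat is given. A positive result after treatment starts leads to unblinding and discontinuation of study drug.
- **Appendix A:** on the page running to Week 56 and again on the page for Weeks 60 to 108, the row label is "Pregnancy test Each visit after V4 for all WOCBP". On both pages the only mark in the row is in the first column, the one that carries informed consent.
- **SAP Section 2.3.3:** its copy of the schedule marks the pregnancy test at Screening only, with no wording about later visits.
- **Section 5.1.1, criterion 9:** a woman of child-bearing potential "must have a negative serum pregnancy test within four weeks prior to the first dose of study drug". Contraception is required while she takes part, then "up to 30 days after the study for WOCBP and up to 90 days for partners of child bearing potential of male participants". The same criterion ends by setting a limit of 28 days after the last dose. The synopsis version has only the 28-day limit.
- **Section 5.2:** pregnancy is the one withdrawal reason labelled mandatory.

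**The concern.** The entry criterion and the mandatory withdrawal rule show that the sponsor does not want a pregnant woman dosed. Whether a pregnancy that nobody suspects would be found during treatment depends on which part of the protocol a site uses. Section 7.6.3, the Appendix A marks and the SAP schedule all point to Screening only. The Appendix A label points to repeat tests, but from a start that a site cannot identify.

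Two moments matter most. One is the run of infusions to Week 24. The other is Week 28, when a woman who was on placebo receives PRM-151 for the first time. Criterion 9 ties the negative test to the first dose of study drug, so it does not require a new test at that point. The HRCT scans at Weeks 28, 76 and 128 add a smaller reason: Section 1.5 assures the reader that pregnant women will not be exposed to study radiation, and under 7.6.3 alone no scheduled test after Screening supports that assurance.

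The contraception wording is a lesser matter. One criterion sets two end points, and the synopsis carries only one of them.

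**Working it through.** The plan gives no figure to reproduce. The check compares the texts and uses simple counts.

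**1. Infusions without a scheduled test, for a site relying on 7.6.3 or on the marks.** Section 5.4 gives dosing on Days 1, 3 and 5, then at Weeks 4, 8, 12, 16, 20 and 24. Infusions = 3 + 6 = 9. Scheduled tests after Screening = 0.

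**2. Age of the last scheduled test at the Week 28 open-label dose, same site.** Screening may be up to 4 weeks before the first dose (Section 5.4 and criterion 9). Maximum age = 4 + 28 = 32 weeks. This uses nominal visit days and ignores the visit windows.

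**3. What the label requires.** Section 5.4 and Appendix A name visits by day and week, and no visit is numbered. There are two candidate meanings.

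- *Visit 4.* The start then depends on whether Screening counts as a visit, and on whether Days 1, 3 and 5 count once or three times. The documents do not say.
- *Version 4.0.* This is the current protocol version. A woman enrolled under it would be tested from Day 1. A woman who had passed Week 28 before her site adopted it would have no test under the label up to Week 28. Adoption dates by site are not given. The list of changes for Version 4.0 mentions birth control for these women but not a testing schedule, so it does not settle the question.

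Neither the number of tests nor the first test date under the label can therefore be derived. What can be said is that a test scheduled at a dosing visit would come before that visit's infusion, because Section 7.10 states: "On all dosing days, dosing will occur after all safety and efficacy assessments scheduled for that visit are complete".

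**4. Gap between the two female contraception end points, in days after the last dose.**

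- If the study is taken to end with the last dose: 30 − 28 = 2 days.
- If it ends at the End of Study visit, 28 ± 3 days after the last dose (Section 5.4): 28 + 30 = day 58, range 55 to 61. The gap is 58 − 28 = 30 days, range 27 to 33.

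**5. Who is tested.** Section 7.6.3 counts a woman as not yet postmenopausal if she "has had menses at any time within the previous 24 months", whatever her age. Criterion 9 uses 24 months up to age 55 but 12 months above it. A woman over 55 whose last menses were 12 to 24 months ago falls under the testing section but outside the entry criterion.

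**The case against.** The strongest reply is that the two testing instructions do not contradict each other. Section 7.6.3 says when a repeat is needed and does not exclude scheduled tests. The label adds scheduled tests, and a site can do both. That is correct. A reader might infer that the protocol forbids routine testing in one place and orders it in another, but the text does not go that far. What remains is that 7.6.3 is silent on a schedule, the label's start cannot be read, and the marks do not carry it out.

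A reader might also want to state how many tests the label requires, or to conclude that it guarantees a fresh test at the first open-label dose. Both need a numbering for V4 that the documents do not supply, and the Version 4.0 reading breaks either claim. Nor can one say that a pregnancy will be missed at one site and found at another; that is possible, not established.

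On contraception, the longer period satisfies both sentences, so a cautious site can comply. The 90-day rule for partners of male participants might be read as having no starting point. The sentence is parallel, however, and the starting point naturally carries over from its first half. The rule is misplaced in a criterion about women, but it is not undefined.

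Finally, few women aged 40 to 80 will be of child-bearing potential. This stands and limits the importance of the point. The documents give no number.

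**Conclusion.** The point holds as a small patient-safety inconsistency. The difference between 7.6.3 and the Appendix A label is plain from the text, and Section 7 makes both operative. For a site that relies on 7.6.3 or the marks, the consequence is no scheduled test over nine infusions and a last scheduled test up to 32 weeks old at the Week 28 open-label dose. That figure assumes Screening at the full four weeks and nominal visit timing. For a site that follows the label, the exposure cannot be sized.

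The two contraception end points are a minor addition: 2 days apart, or about 30 if the study is taken to end at the End of Study visit. The primary analysis, sample size and error rate are untouched.

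**What to change.** **Testing.** In 7.6.3 and Appendix A, state the same schedule: a serum test at Screening; then, for all women of child-bearing potential, a serum or urine test before dosing at each four-weekly dosing visit from Week 4 (Weeks 4, 8, 12, 16, 20, 24, 28 and the extension), at End of Study, and on suspicion. Replace the reference to V4 with the named weeks and mark the cells. If V4 meant Version 4.0, also keep a pre-dose test on Day 1. Use one definition of child-bearing potential throughout.

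**Contraception.** State one female end point in both the synopsis and 5.1.1. It should be no shorter than the longest period now written, 30 days after the End of Study visit, unless the sponsor justifies a shorter one. Counting 30 days from the last dose instead would move the limit from about day 58 to day 30 on that reading, and this should not happen by default. Give partners of male participants their own criterion, with 90 days from the same starting point.

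**Cost.** Protocol and consent wording, plus 7 tests per woman of child-bearing potential up to Week 28 (8 if Day 1 is kept). All fall at existing visits where Appendix A already marks blood samples. At extension visits without blood sampling a urine test is enough. The downside is a few extra low-cost tests for a small number of women.

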7.7. Physical Examination

A complete physical examination is to be performed during Screening and an abbreviated physical exam thereafter. The complete physical examination is to include measurement

of height during Screening. Weight is to be measured throughout the study for use in weight based dose calculations.

Complete physical examinations also will include a review of the following body systems:

- General appearance.
- Head, eyes, ears, nose, and throat.
- Respiratory.
- Cardiovascular.
- Abdomen.
- Neurologic.
- Extremities.
- Dermatologic.

Full physical examinations are to be performed at screening; Abbreviated physical exams are to be performed thereafter.

The findings of each examination are to be documented in the eCRF.

If an abnormality noted on physical examination is considered by the Investigator to be clinically significant, then the abnormality is to be recorded as part of the subject's medical history if occurring prior to start of dosing and as an AE occurring if after the start of study drug administration at Week 0, where the finding represents a change from Baseline. Any worsening of a baseline medical condition during the study should be recorded as an adverse event.

